#### **4. Design & Procedures:**

This study will be a prospective, uncontrolled clinical trial. The study will not be controlled as invasive monitoring of hemodynamics will be performed, allowing clear demonstration of a cause-effect relationship.

This study aims to piggy-back on an elective right heart catheterization (RHC) in subjects with chronic heart failure. The right heart catheterization will be part of the subject's standard of clinical care (SOC). Subjects eligible for this study will be referred to the Duke cath lab for the evaluation of cardiac filling pressures because it is found to be necessary by the outpatient provider. This will occur in the cardiac catheterization lab. Subjects get scheduled for RHC days to weeks (2-3) ahead of their procedure. The eligible subject will be contacted before the study to be informed about the eligibility for the study and basic information about the study will be provided over the phone shortly after they have been scheduled. Subject will be consented in person in the morning of the procedure.

The subject will undergo pre procedural testing as demonstrated below in the flow chart (all part of the clinical study - CS). Besides the RHC (SOC) the subject will undergo an invasive cardiopulmonary exercise with the RHC in place. Baseline evaluation is followed by a regional nerve block (bilateral splanchnic nerves) while the subject is in the catheterization lab. This will be performed by an anesthesiologist experienced in splanchnic nerve blocks.

Figure 2: Study flow chart

[figure not shown]

Table: Study events

Required Assessment	Pre procedure (day of)	Baseline (intra-procedure)	Block	Post Block Procedure	Recovery	24 h after procedure	48 h after procedure	6 Months after Procedure (±14 days)
Vitals (BP, HR, RR, SpO2)	X (SOC)	X (SOC)	X (SOC)	X (SOC)	X (SOC)			
Weight	X (SOC)				X (SOC)			
Orthostatic vitals	X (CS)				X (CS)			
Urine output (continuous recording)	X (CS)	X (CS)	X (CS)	X (CS)	X (CS)			
Valsalva		X (CS)		X (CS)				
Labs: BMP, pro-BNP, urine sodium,	X (SOC/CS)				X (CS)			
Labs (Angiotensin II), Plasma Metanephrines, Vasopressin, Plasma Catecholamines, Lactate		X (CS)		X (CS)				
Dyspnea Questionnaire		X (CS)		X (CS)	X (CS)	X (CS)	X (CS)	
Six minute walk test	X (CS)				X (CS)			
Impedance and lung fluid content measurement		X (CS)		X (CS)				
Heart rate variability	X (CS)	X (CS)	X (CS)	X (CS)	X (CS)			
Echocardiogram		X (CS)		X (CS)				
Invasive CPX		X (SOC/CS)		X (CS)				

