Splanchnic nerve block			X (CS)					
Phone Call						X (CS)	X (CS)	X (CS)

\*Phone call will capture mortality status and number of subject admissions to the hospital since procedure

Following enrollment into the study the subject will undergo the following tests/measurements. A majority of the clinical testing occurs as part of the clinical study (CS) however the main procedure of RHC is standard of care (SOC).

Pre-procedure: Following information will be collected from the subject's charts that will be done as standard of care (SOC). Study specific tests/recordings are also listed below:

- If the subject is female and childbearing potential and has not had a pregnancy test since the arrival to the hospital, a blood pregnancy test will be done (CS). If positive the subject will be excluded from the study.
- Subjects will have strict measurement of urine output (SOC). A urine sample will be sent to the laboratory to check for the sodium concentration (CS). Subjects requiring a foley catheter will have measurements taken at comparable time intervals (SOC).
- Recorded vitals including weight, BP, HR, RR, SPO2 on the day before procedure and within 1h before procedure (SOC) and record heart rate variability using a non-invasive wrist monitor for 5 minutes (CS).
- Orthostatic vitals (5 minutes supine, 1+5 minutes sitting and 1+5 minutes standing) on the day before procedure and within 1h before procedure (CS). Also we will document whether s has symptoms bending over for 10 seconds (bendopnea).
- Labs: Basic metabolic panel (BMP) (SOC), brain natriuretic peptide (BNP) (CS), urine sodium (CS) plasma angiotensin II (CS), plasma arginine vasopressin (CS), plasma catecholamines. This will not require an extra lab draw. Total expected blood loss is <20ml.
- Dyspnea questionnaire using a 7-point Likert scale and Visual Analog Scale (CS)
- Six minute walk test (CS)
- Echocardiogram at baseline and after the block will be performed while the subject is on the cath table (CS). This is considered one continuous echo. This ultrasound test will also be used to look at liver blood flow.
- If the subject is on diuretics medications the scheduling of the medication will be adjusted to minimize interference with the study intervention.

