Before cardiopulmonary exercise begins, the subject will perform the Valsalva maneuver. The subject will sit up on the catheterization lab table, after the intravenous lines have been placed. The subject will have an empty syringe placed in their mouth. He/she will blow into the syringe for 30 seconds. This is the standardized method for performing the Valsalva maneuver (Saxena, M, Journal of American Heart Association, 2018). The intracardiac pressures will be measured continuously during the 30 seconds. Following the Valsalva maneuver, the subject will be placed supine on the stationary bike for cardiopulmonary exercise. Cardiopulmonary exercise testing will include a 20 W initial steady phase during which RHC numbers will be recorded and echocardiogram with liver blood flow will be obtained. This will take up to 7 minutes followed by quick (every 1 minute increase in 20W) ramp to peak exercise. At peak exercise repeat hemodynamics and echocardiography will be obtained.

Subjects will further be monitored with:

[figure not shown]
- Telemetry (SOC)
- ClearSite/CheetahMedical/Sphygmocor/ReDS for continuous non-invasive hemodynamic/lung fluid content recording (CS)
- Continuous urine output (ml/hour) recording if foley is present (SOC)
- A non-invasive wrist monitor/chest band to monitor the heart rate variability

Baseline hemodynamics and exercise CPX will be performed before and after the nerve block detailed below.

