#### Follow up procedures:

Following right heart catheterization and lidocaine splanchnic nerve block the will be observed for monitored in the cath lab holding area for 3 hours following nerve block (SOC).

- Continuous recording of urine output for the procedure day (CS) will be achieved by recording urine output at the beginning of pre-testing, just before the cath lab procedure, just after the cath lab procedure and before the subject leaves home.
- Basic vitals (SOC) and orthostatic vitals (CS) following the cath lab procedure and record heart rate variability using a non-invasive wrist monitor (CS).
- Repeat labs after the procedure before the subject leaves. Pro-BNP, BMP, serum sodium (all CS)
- Labs: Angiotensin 2, plasma metanephrines (if on inotropes), plasma catecholamines, vasopressin, lactate, and urine sodium will be collected immediately before and after the procedure
- Dyspnea questionnaire after nerve block (CS) and again at 48 hours
- Six minute walk test (CS) after the block
- Weight after the procedure.

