#### Blood samples processing:

Some blood samples collected before and after the nerve block (plasma metanephrines, plasma catecholamines, angiotensin II and arginine vasopressin, lactate) will be processed (centrifuged) and stored at -70 degrees Fahrenheit before sent out to an external lab. Storage

duration may vary between weeks to months. Samples will be stored in a research freezer located on the 7th floor of Duke North (cath lab research freezer). As part of the study, we will send blood for study-related laboratory tests to the Mayo clinic and Inter Science Institute. These would include laboratory tests such as metanephrines, vasopressin, catecholamines, and angiotensin. A data transfer agreement is already in place.

Safety endpoints:

- The duration of the anesthetic block is estimated for 12-24 hours. The subject will be monitored for up to 3 hours in the catheterization laboratory/holding area, if there is any concern or evidence of procedure related complications the will be kept overnight in the cath lab holding area. A potentially observed effect of the block to prevent discharge the day of procedure could be orthostatic hypotension. will also be contacted at 48 hours post procedure to ascertain any potentially missed complications. Further the subject's medical chart will be observed for 6 months following study enrollment to evaluate for admissions for heart failure.

Incidence of major side effects has been reported to be <1:1000 and are expected to occur immediately post nerve block. They include:

- Pneumothorax, possibly requiring a chest tube
- Aortic puncture with retroperitoneal bleed or hemothorax
- Spinal cord trauma with possibly paralysis

Incidence of minor side effects like:

- Orthostatic hypotension
- Pain at puncture site and intercostal neuralgia
- Gastrointestinal dysmotility including diarrhea, constipation and abdominal cramping
- Bleeding at puncture site

Efficacy endpoints:

The following efficacy endpoints will be evaluated:

- Primary:
- Improvement in 20 W and peak exercise PA mean and wedge pressure
  - Reduction in central venous pressure and/or pulmonary artery pressure (diastolic) and/or pulmonary capillary wedge pressure at 30 minutes after nerve block

Secondary:

- Reduction in central venous pressure and/or pulmonary artery pressure (diastolic) and/or pulmonary capillary wedge pressure at 30 minutes after nerve block

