- Increase in cardiac output at rest, improvement in echocardiographic parameters like ejection fraction (increase), central venous pressure (decrease), pulmonary artery systolic pressure (decrease), right ventricular diameter (decrease), left ventricular diameter (decrease)
- Reduction in pro brain natriuretic peptide (pro-BNP)
- Increase in UOP (output measured in ml/hour) and renal function (BUN and creatinine) in the hours following the procedure.

- Symptomatic improvement like a decrease in dyspnea (dyspnea questionnaire) and 6-minute walk test

Exploratory aims:

- Change in cardiac and autonomic markers after nerve block (i.e. angiotensin and catecholamines)

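### Neurohormone and lactate draws are timed inconsistently and not tied to rest, so the exploratory before-after change may include an exercise or recovery effect

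*Combined protocol and SAP*

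**What the plan says.** Section 4 of the combined protocol and SAP times these samples in four places, and they differ.

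- **Follow up procedures:** angiotensin, metanephrines (if on inotropes), catecholamines and the rest of the list, ending "vasopressin, lactate, and urine sodium will be collected immediately before and after the procedure".
- **Blood samples processing:** "Some blood samples collected before and after the nerve block", so the anchor is the block.
- **Study events table:** the row "Labs (Angiotensin II), Plasma Metanephrines, Vasopressin, Plasma Catecholamines, Lactate" is ticked under the intra-procedure baseline and the post-block columns. The Valsalva and the invasive exercise test are ticked in the same two columns, and no order within a column is given.
- **Pre-procedure list:** "plasma angiotensin II (CS), plasma arginine vasopressin (CS), plasma catecholamines" appear among labs obtained before the catheterization. The table has no pre-procedure tick for them, and this list omits lactate and metanephrines.

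On exercise, step 1 of the procedure states: "Baseline hemodynamics and exercise CPX will be performed before and after the nerve block detailed below". The test goes to peak: after a 20 W stage, "This will take up to 7 minutes followed by quick (every 1 minute increase in 20W) ramp to peak exercise". The exploratory aim that uses the samples is "Change in cardiac and autonomic markers after nerve block (i.e. angiotensin and catecholamines". Section 14 compares pre and post values by paired t-test at a two-sided 0.05 level, and Section 4 describes the trial as uncontrolled.

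**The concern.** Section 3 itself says that circulating catecholamines rise with physiologic stressors, and a ramp to peak exercise is one. A before-after difference in these markers describes the block only if both samples are taken in the same state relative to exercise. The follow-up wording does not secure this, because *procedure* can mean two things and each places the two draws differently around the exercise tests.

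Section 4 justifies having no control group by the invasive hemodynamic monitoring. That argument does not extend to blood markers drawn at unspecified times around exercise. At stake is whether a reported change in angiotensin or catecholamines can be attributed to the block. Once samples have been drawn at unmatched or unrecorded times, the analysis cannot recover the answer.

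**Working it through.** **1. Order of events.** From the opening of Section 4 and its procedure steps 1 and 2: resting baseline, Valsalva, first exercise test to peak, block, repeat resting hemodynamics, 30-minute break, second exercise test, recovery. The order of baseline and block is explicit: "Baseline evaluation is followed by a regional nerve block (bilateral splanchnic nerves) while the subject is in the catheterization lab". The 30-minute break is stated only before the second test. No recovery interval is stated between the first peak and the block, or before any draw.

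**2. Where the draws fall.**

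| Meaning of *procedure* | Support | Before-sample | After-sample |
|---|---|---|---|
| A: nerve block | Blood samples processing | after first peak test | before second test |
| B: catheterization session | same follow-up list, which uses the word this way for urine output | at rest | after second peak test |
| C: two resting draws | table columns, or the pre-procedure list paired with a post-block draw before the second test | at rest | at rest, though after the first test |

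A and B both follow from the follow-up wording. C is permitted by other parts of Section 4. Nothing in the available text chooses among them.

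**3. Size.** The plan gives no figure to reproduce: no kinetics, no draw-to-exercise interval and no SD for these markers. As an illustration, let peak exercise multiply a marker by *k*, let the excess decay with half-life *h*, and let the block do nothing. Relative to rest, the level *t* minutes after peak is

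L(t) = 1 + (k − 1) × 2^(−t/h).

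Assumed central case: k = 3, h = 10 min, the relevant draw at t = 10 min.

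- L(10) = 1 + 2 × 0.5 = 2.0
- L(25) = 1 + 2 × 2^(−2.5) = 1.354
- L(40) = 1 + 2 × 2^(−4) = 1.125

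Meaning A: both samples follow the same exercise test, so the second is still decaying.

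- Second draw 15 min later: 1.354/2.0 − 1 = −32%
- Second draw 30 min later: 1.125/2.0 − 1 = −44%

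Meaning B: a resting sample against one taken 10 min after the second peak, ignoring any residue of the first test: 2.0/1 − 1 = +100%.

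Range for k = 2 to 4, h = 3 to 10 min and t = 5 to 20 min:

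- Meaning A, gap of 15 to 30 min: about −1% to −61%. The upper end is k = 4, h = 7.2, t = 5, gap 30: 1.103/2.854 − 1.
- Meaning B: about +1% (k = 2, h = 3, t = 20) to +212% (k = 4, h = 10, t = 5: 1 + 3 × 0.707 = 3.12).

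**4. Effect on the test.** Suppose there is no block effect and exercise shifts the paired difference by 0.5 SD of that difference (assumed). The noncentrality is 0.5 × √n. For n = 30 (Section 7 target) it is 2.74 against a critical t of 2.045, and p < 0.05 occurs with probability 75%. For n = 15 (one ejection-fraction group) it is 1.94 against 2.145, giving 44%. The nominal rate is 5%.

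**The case against.** The strongest reply is that the plan may already intend two resting draws. The pre-procedure list includes the two kinds of marker that the exploratory aim names. A sample drawn immediately after the block would come before the second exercise test because of the 30-minute break. The study flow chart (Figure 2) is not reproduced in the text available and might fix the times. This stands in part: it rules out calling the mismatch certain. It does not remove the inconsistency, because the table has no pre-procedure tick for these labs and the follow-up and sample-processing texts would still need to agree with any flow chart.

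A reader might go further and infer that every reading of the plan mismatches the samples, or that the error would produce the very fall the study predicts. The documents support neither. Resting pairs are allowed, and the exploratory aim speaks only of change: no section predicts a fall in circulating catecholamines or angiotensin. Even the sign is unsettled for catecholamines. The injected solution contains epinephrine (procedure step 2), which could raise the post-block value against a recovery-driven fall.

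It is also fair that the range in the working starts near zero, that one decay curve is a crude stand-in for several different markers, and that the aim is exploratory and names neither vasopressin nor lactate.

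**Conclusion.** The concern holds as a defect of specification that can bias a result, not as a demonstrated bias. The draw times conflict across four parts of Section 4 and are not tied to rest in the available text. Either natural meaning of the follow-up wording puts one sample shortly after peak exercise and not the other.

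In the assumed central case, with no block effect, the apparent change is about −32% to −44% if the procedure is the block and about +100% if it is the session. All kinetic inputs are assumptions; the documents supply only the order of events. An uncontrolled paired comparison cannot separate such a shift from a block effect.

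The consequence is confined to the exploratory autonomic-marker aim. The primary and secondary endpoints do not use these samples. Severity is low to moderate.

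**What to change.** Replace the follow-up timing with two supine resting draws through the line already in place:

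- **Baseline:** after line placement and before leg elevation, Valsalva and the first exercise test.
- **Post-block:** at the end of the existing 30-minute break, just before the second Valsalva and exercise test.

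Record the clock times of each draw, of the first peak exercise and of the block. Bring the events table, the pre-procedure list, the follow-up list and the sample-processing text into line with these two points, and check Figure 2 against them. Interpret post-block catecholamines with the injected epinephrine in mind.

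The cost is protocol wording and the draw sheet; no sample or procedure is added. Two small downsides remain. The post-block draw still follows the first exercise test, so some residue may persist: in the assumed central case L(40) − 1 = +12.5% at 40 min after peak, less if the interval is longer. The recorded times let this be examined. In addition, the post-block sample no longer describes the state after exercise.

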  - The subject will be asked to hold the morning diuretic medication and the morning dose will be given 3 hours after the procedure (CS). This is not expected to provide any risk to the stable chronic heart failure subject, especially since the diuretic medication will be resumed after completion of study that same day.
- Other medications can be continued, unless otherwise specified in the exclusion criteria.

Procedure:

1. Subjects will undergo elective right heart catheterization in the Duke catheterization laboratory lab as ordered by the primary team. A

cardiopulmonary exercise test will be added if not already ordered by the primary provider. Central hemodynamics will be recorded (baseline, prior to nerve block) (SOC). The access site for the right heart catheterization will be radial, brachial or cervical (SOC) to allow a prone positioning of the subject for the splanchnic nerve block described in the next paragraph. Additional baseline RHC numbers will be recorded with legs elevated, which is done to simulate a fluid bolus.

If the subject's hemodynamics provide any other concern for complications related to the splanchnic nerve block (such as underfilling or severe pulmonary hypertension, not related to left heart failure) as determined by the study personnel, the splanchnic nerve block and associated monitoring will not be performed. The subject will be considered a screen failure. Any information and samples collected prior to this will be discarded/destroyed per institutional policies.

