2. Unilateral splanchnic nerve block performed by an anesthesiologist (see images below) (CS). The anesthesiologist will perform a unilateral block to the splanchnic nerve. The blood pressure will be checked, after 15 minutes, post-block. If the systolic blood pressure is reduced by  $> 20$ mmHg, the contralateral splanchnic nerve will not be blocked. Following the right heart catheterization procedure the subject will be prone on the abdomen. Central venous access remains in place. Needle will be placed under fluoroscopic guidance in the posterior chest wall. Anesthetic solution (1.5% lidocaine with 1:200,000 epinephrine and of 0.5% ropivacaine) will be injected. Lidocaine 1.5% with Epinephrine 1:200,000 will be used initially to confirm extravascular administration. The subject will then be placed back on his/her back. The subject will then undergo repeat hemodynamic measurement with the RHC catheter that was already in place. Then the subject proceeds with invasive cardiopulmonary testing after a 30 minute break. The central venous catheter will be removed after the hemodynamic monitoring/testing is completed in the catheterization laboratory.

Additional measurements include:

- Orthostatic vitals (CS).
- Dyspnea questionnaire (CS)
- Echocardiography and liver flow measurements (CS)

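### Post-block resting pressures follow one peak exercise test and the post-block walk follows two, with no stated recovery check, while neither baseline follows any peak test

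*Combined protocol and SAP*

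**What the plan says.** Section 4 (Design & Procedures) places the whole first round of testing ahead of the intervention: "Baseline evaluation is followed by a regional nerve block (bilateral splanchnic nerves) while the subject is in the catheterization lab". In procedure step 1, baseline catheter readings come first, then leg elevation and Valsalva, then supine cycling: a steady phase at 20 W of up to 7 minutes and a "quick (every 1 minute increase in 20W) ramp to peak exercise". The section adds that "Baseline hemodynamics and exercise CPX will be performed before and after the nerve block detailed below".

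In step 2 the subject is turned prone, blocked, and turned back. Then "The subject will then undergo repeat hemodynamic measurement with the RHC catheter that was already in place", and the second exercise test follows a 30-minute break.

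The study events table puts the walk test in the pre-procedure and recovery columns. The follow-up list confirms the second one: "Six minute walk test (CS) after the block".

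The efficacy endpoint list names a fall in resting CVP, PA diastolic or wedge pressure 30 minutes after the block, under both primary and secondary. Its first primary item is PA mean and wedge at 20 W and at peak. A secondary item is "Symptomatic improvement like a decrease in dyspnea (dyspnea questionnaire) and 6-minute walk test". Section 14 analyses before-after change by paired t-tests and bases its power statement on CVP.

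**The concern.** A before-after comparison in a single arm attributes to the block everything that happens between the two readings. Section 4 justifies having no control group on the ground that invasive monitoring makes cause and effect plain. That argument needs the pre-block reading to describe the subject just before the block. Here a full exercise test to peak lies between the baseline resting reading and the block, and nothing in the analysis separates recovery from that test from the effect of the block.

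Two results are exposed. The change in resting pressure, a listed primary endpoint that includes the CVP used for power, may contain residual exercise recovery. The walk test, offered as evidence of symptomatic improvement, compares a walk before any peak test with a walk after two.

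**Working it through.** **Order of events, from the section 4 text, the events table and the follow-up list**

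| Step | Event | Peak tests already done |
|---|---|---|
| 1 | Walk test 1 (pre-procedure) | 0 |
| 2 | Baseline resting pressures, leg elevation, Valsalva | 0 |
| 3 | First exercise test to peak | 0 |
| 4 | Prone, block, blood pressure check at 15 minutes | 1 |
| 5 | Post-block resting pressures | 1 |
| 6 | Second exercise test to peak | 1 |
| 7 | Walk test 2 (recovery) | 2 |

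Extra peak tests before the post-block value: resting pressures 1 − 0 = 1; walk 2 − 0 = 2; exercise pressures 1 − 0 = 1.

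**Recovery time in the text**

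- First peak test to block: no interval or criterion stated.
- Block to resting endpoint: 30 minutes in the endpoint list. Step 2 instead describes the repeat reading ahead of the 30-minute break. These two statements need reconciling.
- Second peak test to walk 2: no minimum stated. If the walk falls within 3 hours of the block and the second test starts at least 30 minutes after it, the gap is at most 180 − 30 = 150 minutes, less the length of that test.

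**What a carry-over would do to the paired t-test**

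The plan's own figure is power 0.90 for a 25% fall in CVP with n = 16 and two-sided α = 0.05. It cannot be reproduced, because section 14 gives no SD. Solving backwards with the noncentral t on 15 degrees of freedom gives a standardised effect d = 0.868, so the implied SD of change is 25 / 0.868 = 28.8%. This reads the statement as a paired comparison. Its wording refers to experimental and control groups, which this trial does not have.

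For a shift b (in % of CVP) unrelated to the block, the noncentrality is (b / 28.8) × √n. For example, b = 5 and n = 16 gives 0.174 × 4 = 0.69.

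| Carry-over fall b, no block effect | Rejection rate, n = 16 | Rejection rate, n = 30 |
|---|---|---|
| 0 | 5.0% | 5.0% |
| 2.5 | 6.2% | 7.5% |
| 5 | 10.0% | 15.1% |
| 10 | 25.5% | 45.2% |

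In the other direction, if carry-over masks 5 or 10 points of a true 25% fall, the noncentrality at n = 16 is (20 / 28.8) × 4 = 2.78 or (15 / 28.8) × 4 = 2.08. Power then drops from 90% to 74% or 50%.

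The values of b are assumed. The table shows sensitivity and does not estimate carry-over.

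**The case against.** Several stronger readings are tempting, and the documents do not support them.

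- *That both baselines precede all exercise.* This is true of the walk only. The pre-procedure walk comes before the baseline catheter readings. Both resting readings follow that same walk, so the imbalance is still one peak test.
- *That nothing separates the first peak test from the post-block resting value.* The turn to prone, needle placement under fluoroscopy, injection and a 15-minute blood pressure check come between them, and the endpoint is timed at 30 minutes after the block. Procedure time plus 30 minutes may let most of the effect fade. The interval is nevertheless unspecified as recovery and can differ between subjects.
- *That carry-over is a known share of the planned 25% fall.* Any such share only restates an assumed shift. Nothing in the documents shows that a shift persists this long.
- *That a null walk result can be set aside.* Fatigue would tend to work against the block, which makes an observed gain more convincing. Excusing in advance an unchanged or shorter walk, with no matching caveat for a longer one, would be one-sided.

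Two objections bear on the remedy. A new baseline taken while pressures are still raised would credit their later decline to the block, so it needs a recovery criterion and must not displace the first reading from the report. Nor would it separate the block from prone positioning, injected epinephrine or elapsed time. Both stand and shape the fix.

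Finally, the study flow figure is not shown and may give timings. The absence of a rest interval can be asserted only of the visible text.

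**Conclusion.** The concern holds as a matter of sequence: one extra peak test before the post-block resting pressures, two before the second walk, no recovery criterion in the visible text, and no control arm or model term to separate these from the block. Size and direction are unknown. Resting pressures could move either way, while fatigue would more plausibly shorten the walk. The error rates above rest on the back-calculated SD of 28.8% and on assumed shifts.

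This does not invalidate the study. It is an avoidable source of confounding in a listed primary endpoint, and it should be reduced because doing so is cheap. The same first-versus-second-test order affects the primary endpoint of pressures at 20 W and at peak, and the change below does not resolve that.

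**What to change.** 1. With the catheter in place, record a second supine resting set (CVP, PA diastolic, PA mean, wedge) after the first exercise test and just before the turn to prone. Take it only once a pre-specified return-to-rest criterion is met, for example heart rate and pressures within a set margin of the first reading, or a fixed minimum rest.
2. Use this set as the pre-block value for the resting endpoint. Keep the first reading for the hemodynamic eligibility check, and report the change from both baselines so that the carry-over is visible.
3. Reconcile the step 2 description of the repeat reading, placed ahead of the 30-minute break, with the endpoint defined at 30 minutes after the block.
4. State in the report that the second walk follows two peak tests, so a change in either direction cannot be attributed to the block alone. Do not declare in advance that an unchanged or shorter walk is no evidence against an effect.
5. State as a limitation that the 20 W and peak exercise endpoint compares a first with a second test on the same day.

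Cost: one more set of readings on an indwelling catheter, a few more minutes in the lab (longer if recovery is slow), and wording changes.
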